1) Members of the investigative team have conducted multiple trials of rTMS, including pivotal trials for FDA-approval of TMS for depression ([name] et al., 1997) and in substance using individuals ([name] et al., 2015; [name] et al., 2017; [name] et al., 2017).

2) The investigative team completed a trial in acutely suicidal, depressed Veterans. In that trial we demonstrated the feasibility of delivering an accelerated course of rTMS (the equivalent of 18 sessions over three days), to acutely ill inpatients ([name] et al., 2014). Sixteen of 18 participants in the active group and 20 of 21 in the sham group completed the three day course. These findings demonstrate our team's ability to recruit Veterans into an accelerated rTMS based trial and the feasibility of this treatment paradigm.

Figure 1. Change in craving ± SEM

3) The investigative team also completed a single-blind, sham controlled crossover study demonstrating that a single session of active 10Hz DLPFC TMS acutely decreases self-reported opioid craving and thermal pain sensitivity among opioid use disordered individuals both on and off buprenorphine (Breedlove et al., 2015). In addition to demonstrating that a single session of rTMS may have an effect on both craving (Figure 1) and pain (Figure 2) in this group, this small trial demonstrated that our group is able to feasibly deliver rTMS to this population, with a retention rate of 81% (13/16).

Innovation: This pilot trial is innovative in several respects. 1: This trial will be the first randomized-controlled trial applying multiple sessions of rTMS to a cohort of OUD patients. This is important as it is well established that multiple sessions of rTMS have a larger and more durable effect than single sessions of

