rTMS. Furthermore, it is well known that in order to derive a meaningful clinical effect, the application of multiple sessions of rTMS are needed. 2: This will be the first trial testing an accelerated rTMS treatment paradigm using established rTMS doses in an addictions population. This is important as there is a clear dose response effect in rTMS, where larger doses of rTMS result in a larger clinical effect ([name] et al., 2010; McDonald et al., 2011). It is additionally important as OUD and other substance use disordered populations may be difficult to treat using the standard treatment paradigm of one session per day over several weeks. 3: This trial will be the first to use rTMS as an adjunct to standard of care opioid treatment. OUD patients, including Veterans, are difficult to engage in outpatient care. Subsequently, a treatment that encourages retention and integration early in the recovery process could have a significant impact on patient outcomes.

RESEARCH DESIGN AND METHODS

Approach Overview (Figure 3): Participants will be recruited from the Ralph H. Johnson VAMC, local VA clinics, and Charleston Center. We will collect data at one week, four weeks, and three months following rTMS completion.

[figure not shown]
Acute Phase: We will screen, consent, enroll, and assess participants during an enrollment session. Following enrollment, each participant will complete baseline measurements of opioid use, opioid craving, pain, and functioning (as outlined below). Following the enrollment session, each participant will be randomized and begin the acute treatment phase of the trial. *Participants will receive a total of six sessions of rTMS on three days during the acute phase of the study over a period of up to three weeks. A period of up to one-week in between treatment days will be allowed to maximize feasibility of intervention deliverability in this population while minimizing risk of a treatment gap that is too long to allow for a summation of effect.* On the third treatment day, pain assessments will be repeated. Craving and pain will be assessed using validated questionnaires.

Continuation Phase: Participants will return at one week, four weeks, and three months for follow-up visits to preliminarily assess the intervention's impact on opioid use, pain, and functional outcomes.

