Statistical Analysis: *Study feasibility will be primarily measured by a) the total number of rTMS sessions completed (out of 18 total sessions) b) the proportion of participants completing all of the rTMS session and c) the proportion of participants completing all of the rTMS sessions as well as the follow-up visits. Study tolerability will be measured as the total number of treatment emergent adverse events. Group differences (active rTMS vs. sham rTMS) in the feasibility and tolerability measures will be estimated using generalized linear models with appropriate distributions (Negative binomial for session and AE count and logit for study treatment completion). In addition to study feasibility, efficacy measures (opioid use amounts, pain, and sleep quality) will be estimated for the entire cohort as well as estimates of between group differences. Changes in study efficacy outcomes from baseline to follow-up visits will be estimated and analyzed using appropriate statistical approaches. When parametric modeling assumptions can be made, changes over time and associated variability will be estimated between treatment groups using general linear mixed models (GLMMs). The GLMMs will allow us to estimate group-specific changes over time and overall effect sizes, along with the variation in those measures, while controlling for relevant baseline covariates (e.g. baseline craving, morphine equivalents, withdrawal). Although we will likely not be powered to detect between-group differences in binary outcomes (i.e. any drug use), such effects will be explored using generalized mixed models, and for time-to-event data (e.g. days to first opioid use), survival analysis models will be constructed. When parametric modeling assumptions do not appear to be valid, alternative (e.g. non-parametric) approaches will be used. Efficacy outcomes will also be analyzed for evidence of differential treatment effects in subgroups determined by gender, race, and ethnicity. Post-hoc exploratory analyses using GLMMs within the active rTMS group will address whether specific characteristics (e.g. demographics, baseline craving, morphine equivalents, withdrawal, PTSD) are associated with a differential treatment effect. The subgroup-specific treatment effects and corresponding confidence intervals will be constructed and will be interpreted in terms of their clinical, rather than statistical, significance, and effect size of treatment to inform future trials will be estimated.* **Missing Data and Attrition:** *Missing data in longitudinal studies can be a problematic feature but can be mitigated through study design considerations. We will make every effort to prevent attrition, e.g., telephone/text/e-mail reminders prior to visits, and reinforcing attendance at each visit. However, these methods do not ensure that all data will be collected, and appropriate analysis methods will be employed to accommodate missing data. Maximum likelihood estimation yields valid inferences assuming ignorable attrition (i.e., attrition is accounted for by covariates or the dependent variable measured prior to dropout). In addition, in keeping with the ITT, we will make every effort to continue assessments for the entire course of randomized treatment, even among those who stop participating in the study assigned intervention or fail to complete the full rTMS time course.*

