
Sample Size Justification: A total of n=20 participants (n=10 per arm) will be enrolled. We anticipate that <20% of study participants will withdraw from the study or be lost to follow-up, meaning that $\geq n=16$ participants are expected to complete the study. This sample size should allow us to assess feasibility and tolerability of the intervention, and ensure that group-specific changes will be able to be estimated in a precise fashion, with 95% confidence intervals extending ~ 0.5 standard deviation units. Similarly, the overall effect size confidence interval

will likely extend only 0.3 standard deviation units. As an exploratory and developmental project, we recognize that our final sample size will not result in a fully powered study design. Model based means and variability estimates will be derived from unadjusted and adjusted analyses and will be vital for designing a larger, more definitive trial in the context of a subsequent MERIT submission. **Relapse, Drop-Out and Clinical Deterioration:** Every effort will be made to re-engage participants who miss appointments. Clinical deterioration, such as exacerbation of psychiatric or substance use disorders, will be assessed on a case-by-case basis and appropriate care will be arranged. In the case of suicidal ideation, standard STAR program operating procedures will be followed which entails contact of on-call STAR clinicians. Participants will be considered drop outs if they do not come back for follow-up visits after three attempts to contact. With the exception of participants who formally withdraw from the study, we will attempt to assess early terminators at the time of discontinuation and at the post-treatment time points. These participants will be considered in the intent-to-treat efficacy analyses.

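### The adverse-event count used for tolerability has no exposure term or common counting window, so unequal early stopping could distort the comparison between arms

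*Combined protocol and SAP*

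**What the plan says.** The Statistical Analysis section defines the endpoint in one sentence: "Study tolerability will be measured as the total number of treatment emergent adverse events". Arms are compared with generalized linear models, "Negative binomial for session and AE count and logit for study treatment completion". Neither that section nor any other names an offset, a rate per session or per day, or a period over which AEs are counted for every participant.

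The documents give two accounts of when AEs are collected. In Table 1 the adverse-event row is marked under the stimulation sessions and not under follow-up. Protection of Human Subjects, section 2b, says that AE monitoring covers the whole study.

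The amount of exposure is also stated in two ways. The Acute Phase paragraph says: "Participants will receive a total of six sessions of rTMS on three days during the acute phase". The Statistical Analysis section measures feasibility by "the total number of rTMS sessions completed (out of 18 total sessions"), and section 1c (Potential Risks) also gives 18, spread over 5 days.

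Three provisions bear on participants who stop. The Missing Data paragraph promises efforts to keep assessing them. The paragraph on relapse and drop-out promises attempts to assess early terminators, except those who formally withdraw. That paragraph's intent-to-treat sentence covers the efficacy analyses only and does not mention AEs.

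**The concern.** A raw count combines how often events happen with how long a participant is exposed and observed. If AEs are recorded only at stimulation visits, someone who leaves after the first treatment day has fewer scheduled occasions to report one. The most common expected event, discomfort at the stimulation site, is described in section 1c as occurring while treatment is given, so it is tied to sessions. When one arm attends fewer sessions, its count can be lower at the same per-session rate.

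The Sample Size Justification names tolerability beside feasibility as something the trial should be able to assess, and says that the model-based estimates will be used to design a larger trial. A distorted AE ratio could therefore be carried forward.

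**Working it through.** **The plan's own figure.** The only stated figure on early loss is in the Sample Size Justification: "A total of n=20 participants (n=10 per arm) will be enrolled" and "We anticipate that <20% of study participants will withdraw from the study or be lost to follow-up". At 20% loss, 20 × (1 − 0.20) = 16, which reproduces the plan's 16 or more completers. This figure concerns loss from the study, not incomplete treatment, and is not split by arm. No AE rate, dispersion or power for tolerability is given.

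**Inputs from the documents.** 10 per arm. Completion in the team's earlier accelerated trial (Preliminary Studies, item 2): "Sixteen of 18 participants in the active group and 20 of 21 in the sham group completed the three day course".

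**Assumed, not in the documents.** Stoppers receive a fraction f of the course, with f = 1/3 as the central case and 0 to 2/3 as the range. Within an arm, stoppers and completers have the same per-session AE rate.

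**Formula.** With completion proportion c, the mean share of the course received is e = c + (1 − c) × f. The expected count ratio equals the per-session rate ratio multiplied by e(arm with more stopping) / e(other arm). Only the fraction f enters, so the factor is the same for six or 18 planned sessions.

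| Stopping, arm A v arm B | e(A) at f = 1/3 | e(B) at f = 1/3 | Factor | Range, f = 0 to 2/3 |
|---|---|---|---|---|
| 2/18 v 1/21 (earlier trial) | 0.926 | 0.968 | 0.956 | 0.933 to 0.978 |
| 2/10 v 0/10 (assumed) | 0.867 | 1.000 | 0.867 | 0.80 to 0.93 |
| 3/10 v 1/10 (assumed) | 0.800 | 0.933 | 0.857 | 0.78 to 0.93 |
| 4/10 v 0/10 (assumed) | 0.733 | 1.000 | 0.733 | 0.60 to 0.87 |
| 2/10 v 2/10 (assumed) | 0.867 | 0.867 | 1.000 | 1.00 |

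In the 4/10 v 0/10 case a true per-session rate 1/0.733 = 1.36 times higher would look equal.

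**Check by simulation.** Negative binomial models were fitted with 10 per arm, assuming 1/3 AE per session, dispersion 0.5, six sessions, stoppers leaving after two, and equal true rates. The median ratio without an offset was 0.72 (4/10 v 0/10) and 0.87 (2/10 v 0/10). With a log(sessions) offset it was 0.985 and 1.00.

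**Comparison with sampling error.** The standard error of the log ratio is √[2 × (1/(10m) + k/10)], for mean m AEs per participant and dispersion k, both assumed. For m = 3, k = 0 it is √(2/30) = 0.26. For m = 0.5, k = 1 it is √(2 × 0.3) = 0.77. The log bias is ln 0.956 = −0.045 at the earlier completion rates and ln 0.733 = −0.31 in the extreme split.

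**If AEs are not proportional to sessions.** Take 4/10 v 0/10, with stoppers leaving after the first of three treatment days. If AEs fall 50/30/20% over the days, the raw ratio is (6 + 4 × 0.5)/10 = 0.80 and the offset gives 0.80/0.733 = 1.09. If all fall on day 1, the raw ratio is 1.00, which is correct, and the offset gives 1.00/0.733 = 1.36.

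**The case against.** The strongest reply is that the effect is conditional and probably small. It needs stopping to differ by arm. The only completion rates in the documents differ by one extra stopper (2/18 v 1/21, Fisher two-sided p about 0.59) and give a factor of 0.96. The larger figures come from assumed splits; 4 of 20 stopping is exactly 20%, whereas the plan anticipates less than that for study loss. All of this stands.

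A reader might infer that someone who stops because stimulation is intolerable necessarily contributes fewer AEs than someone who tolerates every session. The documents do not support that. Such a participant normally has at least one AE, and a participant who tolerates everything may have none. The factors above assume that stopping is unrelated to a participant's AE rate; AE-driven stopping would change them.

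A reader might also infer that the plan expects unequal exposure because it compares session counts by arm. It measures them as a feasibility outcome, which is not a prediction, and reporting them lets a reader see an imbalance.

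A third tempting inference is that an offset should replace the raw count. A total count by randomised arm over a fixed window is a legitimate summary. Section 1c says that intensity is ramped up over the first three sessions and that participants get used to stimulation quickly, so a constant per-session rate is doubtful and the offset can over-correct.

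Some safeguards exist: assessment is to continue after stopping where possible, and the AE record captures whether the intervention needs to be changed or stopped. These do not settle the point. Table 1 still shows no AE collection at follow-up, formal withdrawals are excepted from continued assessment, and no common window is fixed.

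**Conclusion.** The gap is real but modest. The plan compares raw AE totals with no exposure term, and its two accounts of AE collection leave the counting window undefined. If stopping differs between arms and AEs accrue or are recorded with sessions, the ratio understates the AE rate in the arm that stops more. The understatement is about 2 to 7% at the team's earlier completion rates and reaches 27% (factor 0.73) only in an assumed 4/10 v 0/10 split with stoppers receiving one third of the course. With equal stopping it is nil.

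It would go too far to say that the endpoint is biased as it stands, or that it will flatter the less tolerable treatment. Nothing in the documents shows that stopping will differ by arm, and sampling error at 10 per arm will usually be larger than the distortion. Nor is tolerability plainly one of two main objectives: the end of the Background and the summary in the Data and Safety Monitoring Plan state the aim as feasibility and acceptability. This is an inexpensive improvement, not a reason to abandon the planned count.

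**What to change.** 1. Keep the raw AE count. Define one counting window for all randomised participants, including those who stop, and align Table 1 with section 2b so that AEs are collected throughout that window.
2. Beside the count, report by arm: AEs per session received, from the same negative binomial model with a log(sessions received) offset among participants with at least one session; the proportion with at least one AE; and discontinuations due to AEs.
3. Label the per-session model as supporting. State that it assumes a roughly constant AE rate per session and over-corrects if AEs are concentrated early.
4. Reconcile the planned session total between the Acute Phase paragraph (six) and the Statistical Analysis section and section 1c (18), so that exposure is defined.

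The cost is one extra model term, two simple summaries and an AE row at the existing follow-up visits. No additional participants or visits are needed. The downside is a second AE ratio that may differ from the first, which is why its supporting role should be fixed in advance.

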Screening and Eligibility Assessment: Individuals will be screened by the research study intake coordinator. An initial pre-screen focused on inclusion/exclusion psychiatric diagnoses, medical status, current medication regimen, and ability and willingness to commit to completion of study procedures will be used to initially determine potential study eligibility. Interested individuals will be given a full description of the study procedures and asked to read and sign an IRB-approved informed consent form before participating in a detailed, comprehensive screening and assessment phase. To ensure subjects are not experiencing any acute effects of alcohol, individuals whose breath or saliva alcohol concentration reading exceeds the instruments margin of error (0.002%) will not be allowed to participate until their BAC is not detectable.

Diagnostic/Descriptive Assessment: The *M.I.N.I. International Neuropsychiatric Interview 7.0 for DSM 5* will be used to assess psychiatric and substance use diagnoses, including assessment of opiate use. A medical history will be collected to ensure that the individual is eligible to participate, and the VA medical record may be reviewed to verify medications. In the event that an individual is found to be ineligible, he or she will be given an appropriate referral for further medical or other necessary care. If the individual is eligible, he or she will fill out questionnaires and provide a urine sample to verify self-report of substance use. If female, the urine will first be tested for pregnancy. If the pregnancy test is negative or the individual is male, the urine will be tested for drugs of abuse. A randomization/initial rTMS visit will be scheduled.

Figure 3

rTMS=Repetitive Transcranial Magnetic

Treatment Assignment: Eligible individuals will be randomized to receive active rTMS or sham treatment. Participants will be randomized using a stratified permuted random block design with block sizes of 2 and 4; *this will be utilized to maintain treatment assignment balance throughout the treatment enrollment period based on concomitant pain medication use (yes/no).*

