c. Potential Risks and Risk Mitigation Strategies:

Potential risks of rTMS: The use of high frequency rTMS has been FDA approved for the treatment of major depressive disorder since 2008. Our stimulation parameters (3000 pulses, 10Hz, 5-Seconds on 10-Seconds off) are nearly identical to the FDA approved protocol (3000 pulses, 10Hz, 4-Seconds On, 8-Seconds off), and have been used safely in many investigations including those in depression, pain, and addictions. We chose to use the slightly longer train duration of 5-seconds rather than 4-seconds due to its safety and efficacy in many trials including our preliminary single session trial with opioid users.

The common clinical dose of rTMS in depression is 36 treatments with 3000 pulses per treatment, for a total of 108,000 pulses. We will deliver a total of 18 treatments over 5 days with 3,000 pulses per treatment, for a total of 54,000 pulses. We subsequently will be giving a substantially lower total dose to each participant than is commonly given to patients being treated for depression. Accelerated treatment paradigms (including those with 6 treatments delivered daily) have been safely delivered in both depression and addictions populations without any clear adverse effect.

Risk of Seizure: The most serious risk associated with the use of rTMS is seizure. Since the adoption and widespread use of standard safety guidelines in 1997, there has only been one documented seizure. The risk of seizure has been estimated to be less than 0.1% which is lower than the risk of seizure associated with pharmacologic antidepressants. The risk of seizure is related to the various stimulation parameters (intensity,frequency, train duration), location of application, pre-existing risk of seizure, and substance/medication factors. In the very rare event a seizure is caused, removing the coil is typically sufficient to stop the seizure, and there is no increased risk of subsequent seizure. In order to mitigate the risk of seizure we will carefully individualize the intensity of stimulus (by performing a resting motor threshold determination), treat using standard treatment protocols (used safely in other studies), and exclude potential participants at higher risk of seizure (those with a past history of seizures, those in withdrawal from alcohol or benzodiazepines, etc).

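### The negative binomial for sessions completed gives a poor model-based interval for a capped count, and the completion logit has no fallback if an arm is 10/10

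*Combined protocol and SAP*

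**What the plan says.** The Statistical Analysis section lists three primary feasibility measures: (a) "the total number of rTMS sessions completed (out of 18 total sessions"), (b) the proportion completing every session, and (c) the proportion completing every session and the follow-up visits. Group differences are to come from generalized linear models, with the distributions given in brackets: "Negative binomial for session and AE count and logit for study treatment completion".

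The session maximum differs between sections. Statistical Analysis has 18. The risk section agrees on the number: "We will deliver a total of 18 treatments over 5 days with 3,000 pulses per treatment, for a total of 54,000 pulses". The Acute Phase paragraph has 6: "Participants will receive a total of six sessions of rTMS on three days during the acute phase of the study".

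On size, Sample Size Justification says "A total of n=20 participants (n=10 per arm) will be enrolled" and, with under 20% loss, that at least 16 "participants are expected to complete the study. This sample size should allow us to assess feasibility and tolerability of the intervention".

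The only fallback comes later in Statistical Analysis, after the efficacy mixed models: "When parametric modeling assumptions do not appear to be valid, alternative (e.g. non-parametric) approaches will be used". It names no method and no trigger.

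**The concern.** Sessions completed cannot exceed the number scheduled. When most participants attend everything, the counts pile up at the maximum and their variance can fall well below their mean. The negative binomial has no upper bound and has variance at least equal to its mean. Faced with such data, it fits at its Poisson limit and reports more uncertainty than there is.

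Completion has a different problem. With 10 per arm and high completion, an arm may well be 10/10. Maximum likelihood then gives no finite odds ratio and no usable Wald interval.

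At stake are the planned between-arm contrasts on the primary feasibility measures. Sample Size Justification also says that model-based means and variability will be used to design the next trial.

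**Working it through.** **Inputs from the documents.** 10 per arm; session maximum 6 or 18; expected completion at least 20 × (1 − 0.20) = 16 of 20, which reproduces the plan's figure. Guides from Preliminary Studies: 13/16 retained in a single-session crossover, and 16/18 active and 20/21 sham completing a three-day accelerated course.

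**Assumptions.** The documents give no stopping pattern. I took three equal treatment days, so a non-completer has one third or two thirds of the maximum. Three patterns were used: all stop after day 1, all after day 2, or an equal mix. Both arms have the same completion rate. The 18-session results also rest on three equal days, although the risk section says 5 days.

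**Sessions, one case by hand** (maximum 6, 80% completing, the rest stop after day 1 with 2 sessions):
- Mean = 0.8 × 6 + 0.2 × 2 = 5.2. Variance = 0.8 × 0.2 × (6 − 2)² = 2.56. Variance/mean = 0.49.
- Smallest standard error (SE) of the log ratio that the negative binomial can give, with dispersion zero: √(2/(10 × 5.2)) = 0.196.
- Large-sample SE of the log ratio: √(2 × 2.56/10)/5.2 = 0.138. Ratio 0.196/0.138, about 1.4.

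**Sessions, all cases.** I enumerated all 66 × 66 outcomes exactly. The negative binomial was fitted by maximum likelihood, with SE = √((1/m₁ + a)/10 + (1/m₂ + a)/10), where m₁ and m₂ are the arm means and a is the dispersion. Entries are the mean model SE divided by the true SD of the log ratio, at 70 / 80 / 90% completing, with coverage of the 95% Wald interval.

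| Maximum | All stop after day 1 | Equal mix | All stop after day 2 |
|---|---|---|---|
| 6 | 1.16 / 1.38 / 1.91 (97.4-99.9%) | 1.49 / 1.76 / 2.43 (99.6-100%) | 2.51 / 2.92 / 3.95 (100%) |
| 18 | 1.01 / 1.02 / 1.17 (94.7, 92.7, 95.1%) | 1.01 / 1.09 / 1.42 (94.0, 95.6, 98.7%) | 1.45 / 1.69 / 2.28 (99.4-100%) |

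At 80% with the equal mix, the dispersion sits at zero in 100% of outcomes with 6 sessions and in 68% with 18.

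**Mean width of the 95% interval for the difference in mean sessions.** Welch widths leave out trials with both arms entirely at the maximum.
- 6 sessions, 80%, mix: negative binomial 4.07, Welch 2.40.
- 18 sessions, 80%, mix: 7.5 against 7.2.
- 18 sessions, 70%, day-1 stops: 9.95 against 10.32.
- 18 sessions, 80%, day-2 stops: 7.18 against 4.53.

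**Completion.** The chance that at least one arm is all or none is 1 − (1 − [p¹⁰ + (1 − p)¹⁰])²: 5.6% at 70%, 20.3% at 80%, 23.5% at 13/16 and 57.6% at 90%. With exactly k non-completers among 20 and no arm difference, it is 2 × C(10,k)/C(20,k): 8.7% for k = 4, 21.1% for k = 3 and 47.4% for k = 2. At the accelerated-course rates, the chance that at least one arm is 10/10 is 1 − (1 − 0.308)(1 − 0.614) = 73%.

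The figure of at least 16 refers to completing the study, which is closest to measure (c). Measure (b) cannot have fewer completers.

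A plain logit fitted to 10/10 against 8/10 returns a log odds ratio near 21 with SE about 15,000, so there is no finite estimate.

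**The case against.** The best case for the plan has five parts.

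- **The estimate is unaffected.** A reader might infer that the negative binomial distorts the comparison of sessions. It does not. With a log link and a group term, each fitted mean is the arm's sample mean, so the unadjusted ratio is exact. Only the interval is affected. This stands.
- **The plan does not prescribe a model-based SE for these measures.** With a small-sample robust SE on the same model, the ratios are 0.91-1.00 and coverage 93.8-99.1% over both maxima (trials with both arms at the maximum counted as covered). This stands too: the model can be kept. But the plan does not state a robust SE.
- **The analysis section says 18, not 6.** A reader might infer that the SE is always too large. On 18 sessions it is about right at 70-80% completing with day-1 or mixed stops, and coverage there falls as low as 92.7%. The sessions half therefore depends on which maximum applies and on when people stop.
- **Variance need not be below the mean, even with 6 sessions.** If 80% complete and every non-completer attends nothing, variance/mean is 1.20, though the fitted SE is still about 1.16 times too large. The protocol makes this unlikely, since "A randomization/initial rTMS visit will be scheduled" combines randomization with the first treatment.
- **The plan allows alternatives.** The fallback sentence helps only in part. Its position suggests efficacy outcomes, and it names nothing for a capped count or a 10/10 arm.

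**Conclusion.** The point holds as a minor one. With 6 sessions and 70-90% completing, the model-based SE is 1.2 to 4 times too large and coverage is 97-100%. With 18 sessions it ranges from about right to 2.3 times too large. These figures rest on the assumed stopping patterns and on a model-based Wald interval. The completion problem does not depend on the session maximum: an odds ratio that is not finite has a chance of 20% at 80% completing and 58% at 90%.

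A reader might go further and conclude that the trial cannot report feasibility. The documents do not support that. Per-arm counts and proportions are unaffected, the interval error is mostly conservative, no feasibility decision threshold is set, and the plan says that it is not fully powered.

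**What to change.** Reconcile the session maximum across Acute Phase, Statistical Analysis and the risk section. Keep the negative binomial for adverse event counts, which have no fixed maximum.

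**Sessions.** Report the distribution and mean by arm. Give the between-arm contrast with a variance that respects the maximum: either a small-sample robust (sandwich) SE on the planned log-link model, which allows covariates, or the difference in means with a Welch interval. If both arms are entirely at the maximum, give counts without an interval. If exactly one arm is, flag the interval as unreliable.

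**Completion.** Report each arm's proportion with a Clopper-Pearson interval, and the risk difference with a Newcombe interval (10/10 against 8/10: −0.11 to 0.51). If an odds ratio or covariate adjustment is wanted, use Firth logistic regression (same data: 6.2, 95% CI 0.43 to about 900).

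**Cost.** Wording and a few lines of code; no new data. There are downsides:
- With 18 sessions the Welch interval can be slightly wider than the negative binomial one (10.3 against 10.0 at 70%, day-1 stops).
- No session interval is given when both arms are at the maximum: 0.8²⁰ = 1.2% of trials at 80% completing and 0.9²⁰ = 12.2% at 90%.
- Welch otherwise covers 95.1-99.7% overall in the settings tried, but only 64-93% when exactly one arm is at the maximum at 70-80% completing.
- Newcombe is slightly conservative (97.0% at 80%, 99.1% at 90%) and unadjusted.
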